4.4. Educational intervention

The IG women will receive an intervention based on the use of a web-app with a duration of 12 weeks, which will be complementary to the preventive activities carried out in the health area. The CG participants will not have access to the web-app during the 12 weeks that the intervention lasts and will only receive the usual health care.

The design and evaluation of the intervention is based on the Behavior Change Wheel (BCW)⁸² model and the web-app will be used as the central axis of the same.

The web-app will consist of 6 sections: information related to BC risk factors; self-exploration; feeding; physical activity; news and community the risk factors section will be merely informative. It will collect information in relation to the modifiable and non-modifiable factors that increase the risk of developing this tumor.

The self-examination section will include information related to the signs compatible with the CM and an explanatory video on how to perform the examination of your breasts. This information will enable women to identify the symptoms and signs that are consistent with the onset of cancer.

The food will be subdivided into 3 sections: nutritionist; recipes; tips. A nutrition expert will provide information in the form of videos about the characteristics of a healthy diet. In the recipes section, information related to healthy recipes will be provided. Finally, the advice section will be included where information obtained from secondary sources will be provided.

The physical activity section will also be subdivided into 3 sections: your 30 minutes; routes; options in your environment. First, information will be provided about the importance of doing 30 minutes of physical activity a day, indicating "walking" as an essential activity. In addition, 4 videos will be included with routines that women can perform at home. The routes section will include links to the pages of the municipalities belonging to the VII health area where the routes that can be taken in the area appear. The last section will include the health assets that women can find in the basic health

area (parks, sports spaces, walks...) with basic information about the type of activity that can be carried out in each of them.

Links to resources related to any aspect that may be of interest to the participants will be uploaded in the news section.

Finally, the community section will have a blog structure through which participants will be encouraged to make contributions (routes, recipes, information...) that may be of interest to the rest of the participants. This information will not be public until it is validated by the members of the research team.

5. STATISTICAL ANALYSIS

Initially, the normality of the distribution of the variables will be verified, the Kolmogorov-Smirnov test will be used. A description of the variables will be made using percentages, means (standard deviation) or median (interquartile range) depending on their nature and distribution.

To determine the association between variables, the chi-square test, McNemar for qualitative variables, will be used. For qualitative variables, they will be determined based on the distribution of variables.

Linear regression analyzes will be carried out to determine which variables best predict the score after the intervention in terms of knowledge about risk factors, signs-symptoms of early detection of breast cancer, knowledge and adherence to healthy behaviors.

The analyzes will be carried out using the IBM SPSS version 24.0®, considering that the results were statistically significant when the value of p is ≤ 0.05 .

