4.2. Study population

It will be made up of women belonging to the VII health area of the Principality of Asturias, aged between 25 and 45 years, without a previous diagnosis of BC.

All women who give written consent to participate in the study will be included. Those who: (i) do not have adequate physical or psychological characteristics to participate in the study will be excluded; (ii) do not have the means to regularly access the web-app that will be used to carry out the educational intervention; (iii) your contact by email is not possible.

The recruitment of women will be carried out, between the months of January and February 2022, by sending a letter of invitation to participate from the health area. A random sample of 361 women will be sufficient to estimate, with 95% confidence and an accuracy of +/- 5 percentage units, a population percentage that is expected to be approximately 75%. The percentage of necessary replacements has been predicted to be 20%.

The health area VII technician and member of the research team ([name]) will draw up a list of all the women likely to be included in the study. The members of the research team prepare a letter for each of the women and they will be sent from the management of Sanitary Area VII to the women by postal mail.

The letter contains a contact email to which they will write if they are interested in participating. The women will be answered as the emails are received and when we have obtained the necessary sample, the project will be explained in detail with an information sheet that they may have at their disposal and they will be given their consent informed, which they will sign by selecting the box "I wish to participate voluntarily" that will appear at the end of the consent. Finally, they will be asked for a username and password to access the web-app. In other words, the user or pseudonym to access the web-app will be selected by the woman herself.

The selected women will be distributed, in March 2022, between the intervention (IG) and control (CG) groups using the simple randomization method and with a 1:1 ratio.

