4.3. Data collection: tools and procedure

The data collection will take place during the months of March (pre-test) and June 2022 (post-test). At both times it will be done virtually, using a digital form. Participants will access this form through the project's web-app. The pre-test collection will be carried out after signing the consent and the post-test, after the educational intervention, that is, at 12 weeks.

At both moments, information will be collected related to personal, anthropometric, and behavioral variables (diet and physical activity), self-examination, knowledge related to risk factors and symptoms of breast cancer, perception of risk of developing breast cancer, and barriers to carry out. take actions to prevent it.

Additionally, after the educational intervention, satisfaction with the use of the web-app will be evaluated.

The information on the behavioral variables will be recorded using the Motiva.Diaf questionnaire. It includes 12 items that measure adherence to and motivation to carry out recommendations related to nutrition (questions 1 to 7) and physical activity (questions 8 to 12). Each item presents a Likert-type response format with a range from 0 (lack of motivation to make the recommendation) to 5 (intrinsic motivation). In addition, each separate recommendation can be interpreted dichotomously (makes=1 or does not make the recommendation=0). Finally, the synthetic variable adherence to healthy recommendations is elaborated as a result of scoring each item in its dichotomous interpretation (range 0=worst adherence to healthy recommendations to 12=greatest adherence to healthy recommendations).

The self-examination is carried out by means of the question, do you perform the breast self-examination once a month.

The information related to knowledge, risk perception and barriers with the MARA questionnaire. This questionnaire, specifically related to breast cancer, consists of 31 items that measure the following constructs: knowledge related to risk factors (9 items), knowledge related to signs and symptoms (9 items), perception of risk of developing breast cancer breast (6 items) and perceived barriers to carry out prevention strategies (7 items). Items related to knowledge have a score of 0 (error) and 1 (correct), therefore the range of scores, both for risk factors and for signs and symptoms, is between 0 and 9. The score of the other two scales is represented on a Likert-type scale ranging from 1

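### No between-arm analysis of the yes/no outcomes is planned that uses each woman's own pre-test answer; adding it is a free gain in precision, of a size that depends on figures the documents do not give

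*Combined protocol and SAP*

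**What the plan says.** Section 5 (Statistical analysis) deals with categorical outcomes in one clause: "the chi-square test, McNemar for qualitative variables, will be used". The next sentence says qualitative again, presumably a slip for quantitative, and names no test. The only regression is linear, for post-intervention scores (knowledge and adherence). No logistic, Mantel-Haenszel or other baseline-adjusted method is named for a yes/no outcome. The significance rule is "considering that the results were statistically significant when the value of p is ≤ 0.05".

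Section 4.3 defines the yes/no outcomes. Self-examination is a single question, "do you perform the breast self-examination once a month". For the 12 Motiva.Diaf items, "each separate recommendation can be interpreted dichotomously". Both are collected in March and again in June 2022. Section 3.2.2 makes the post-intervention comparison of adherence between the two groups a specific objective.

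Section 4.2 allocates women "using the simple randomization method and with a 1:1 ratio", so allocation is not stratified by pre-test behaviour.

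**The concern.** A woman's pre-test answer is likely to be the best single predictor of her post-test answer to the same question. The two named tests split the task in a way that leaves this unused where it matters. McNemar pairs the two answers but stays inside one arm, so it yields no IG-CG effect. Chi-square can compare the arms, but a post-test table of arm by answer has no place for the earlier answer. The linear regression is for scores and does not cover these outcomes.

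What is at stake is the width of the interval and the power for self-examination and any single recommendation reported. With simple randomisation, pre-test habits will also differ somewhat between arms by chance, and an unadjusted post-test difference carries part of that difference into this trial's estimate.

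**Working it through.** **Inputs from the documents.** Section 4.2: "A random sample of 361 women will be sufficient to estimate, with 95% confidence and an accuracy of +/- 5 percentage units", for "a population percentage that is expected to be approximately 75" per cent. Also in 4.2: "The percentage of necessary replacements has been predicted to be 20" per cent, and 1:1 allocation. Section 5: significance at 0.05 (taken here as two-sided, which is not stated).

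**Inputs assumed.** The documents give no between-arm difference, target power or phi. Three pairs of post-test percentages (CG vs IG) are used: 60 vs 75, 40 vs 55 and 75 vs 87. The pre-test rate equals the CG rate, and phi runs from 0 to 0.6.

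**Step 1: the plan's own figure.** n = z²p(1−p)/d² = 1.96² × 0.75 × 0.25 / 0.05² = 288.1. Dividing by 1 − 0.20 gives 360.1, rounded up to 361. The figure reproduces. It is a precision size for one percentage, not a between-arm calculation. Losing 20% of 361 leaves 361 × 0.8 = 288.8, so 289 completers, or 144.5 per arm.

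**Step 2: post-test chi-square.** SE = √{[p₁(1−p₁) + p₂(1−p₂)]/144.5}; power ≈ Φ(difference/SE − 1.96). For 60 vs 75: SE = √(0.4275/144.5) = 0.0544, half-width 1.96 × 0.0544 = 10.7 points, power = Φ(0.15/0.0544 − 1.96) ≈ 79%.

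**Step 3: adjusting for the pre-test answer, with phi the same in both arms.** The SE is multiplied by √(1−phi²). Power in per cent:

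| CG vs IG | chi-square | phi 0.2 | phi 0.3 | phi 0.4 | phi 0.5 | phi 0.6 |
|---|---|---|---|---|---|---|
| 60 vs 75 | 79 | 80 | 82 | 85 | 89 | 93 |
| 40 vs 55 | 73 | 75 | 77 | 80 | 85 | 90 |
| 75 vs 87 | 75 | 77 | 79 | 82 | 86 | 91 |

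The half-width for 60 vs 75 falls from 10.7 points to 9.8 (phi 0.4) and 8.5 (phi 0.6). Simulation with a robust-SE risk-difference model agrees: gains are about 2-4 points at phi 0.2-0.3 and about 7-17 at phi 0.4-0.6. At phi 0, the adjusted and unadjusted results coincide within simulation error.

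**Step 4: the effect pattern matters.** Equal phi in both arms is not a neutral assumption. For 75 vs 87 at phi 0.6 it implies that, among women who said yes at pre-test, the share still saying yes is 0.75 + 0.6 × 0.25 = 90% in CG. In IG it is 0.87 + 0.6 × √(0.75 × 0.25 × 0.87 × 0.13)/0.75 ≈ 99%. Part of the effect is then placed on women already doing the behaviour. If the whole effect falls instead on women who said no at pre-test, the simulated gains at phi 0.4-0.6 shrink to about:

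- 60 vs 75: 2-8 points
- 40 vs 55: 4-10 points
- 75 vs 87: 0-7 points

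**Step 5: validity.** In simulations with no effect, type I error was 4.6-5.5% for chi-square, a test stratified on the pre-test answer and the adjusted risk difference.

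**Step 6: chance imbalance.** At an assumed 75% pre-test rate, the SD of the pre-test difference between arms is √(2 × 0.1875/144.5) = 5.1 points. A difference above 5 points in either direction therefore occurs in about one trial in three. At phi 0.5, about half of it carries into the unadjusted post-test difference.

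**The case against.** **The wording of section 5 is open.** It names the tests without saying which table chi-square is applied to. It could, for instance, be used to compare categories of pre/post change between arms. This stands: a reader might infer that the plan expressly commits to an unadjusted post-test comparison, and the text does not go that far. What can be said is that no named method adjusts the arm comparison for the pre-test answer.

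**The test is not wrong.** This stands too. A reader might take chance imbalance to mean bias or an inflated error rate. Randomisation makes the unadjusted test valid on average, and its 5% error rate already allows for chance imbalance. The loss is of precision.

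**The outcomes are secondary in weight.** Most specific objectives map to scores. The 0/1 reading of single items is offered as an option, and the items are then summed to a 0-12 score. Self-examination has no objective of its own. The percentage behind the sample size is not tied to any variable, so it does not show that a yes/no outcome is the main one. This limits the priority but does not remove the point. Self-examination is measured at both times and has its own section in the web-app (section 4.4), and adherence to recommendations is compared between arms.

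**The gain may be small.** Correct at low phi, or where the effect acts on non-adherent women only, which is plausible for an educational intervention. It is also smaller where chi-square power is already high: at 75 vs 90, where power is 92-97%, the gain is 1-7 points.

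**Conclusion.** The point holds as a free improvement. For yes/no outcomes the plan names no between-arm analysis that uses a pre-test answer already collected, and a post-test chi-square is then less precise than the data allow.

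With 289 completers and post-test differences of 12 to 15 points, the gain in power is:

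- about 2-4 points at phi 0.2-0.3 with equal phi in both arms;
- about 7-17 points at phi 0.4-0.6 with equal phi in both arms;
- about 0-10 points at phi 0.4-0.6 if only women answering no at pre-test are affected;
- essentially nothing gained or lost near phi 0.

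A reader might take the 7-17 points as a cost built into the plan. The documents do not support that: they give no effect, power or correlation, and the range needs both a moderate to strong phi and a particular effect pattern. Nor do these figures show that the trial is underpowered, since no between-arm target is stated to measure them against. The adjustment also presumes that the pre-test form is completed before a woman knows her arm; the documents place both the form and the allocation in March.

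**What to change.** Add one sentence to section 5. For monthly self-examination and each single recommendation reported as 0/1, the post-test answer is modelled on allocated arm and the same woman's pre-test answer (logistic or binomial model with robust standard errors). The adjusted risk difference, IG minus CG, with its 95% CI is the between-arm result. If the model is logistic, obtain the risk difference by averaging predicted risks over all women under each arm, so that a conditional odds ratio does not become the headline. Keep chi-square as the unadjusted table and McNemar as within-arm description.

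The cost is that sentence and one extra model per outcome: no new data and no more participants. Fixing it in advance also removes a later choice between adjusted and unadjusted results.

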3.2.2. Specific Objetive

- Evaluate adherence to behavioral recommendations before and after after the educational intervention for each group separately.
- To compare adherence to behavioral recommendations after the intervention between the intervention and control groups.
- Evaluate, in each group separately, the knowledge in relation to the risk factors and symptoms of breast cancer before and after the intervention.
- To compare the level of knowledge in relation to the risk factors and symptoms of breast cancer between the intervention and control groups before and after the intervention.
- Estimate the risk and self-perception of developing breast cancer before and after the intervention for each of the groups.
- To compare the risk and self-perception of developing breast cancer between the intervention and control groups after the educational intervention.

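### Section 5 commits to no between-arm analysis of the scores: it names no test for them, and its only model need not contain study group or the pre-test score.

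*Combined protocol and SAP*

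**What the plan says.** Section 3.2.2 sets three between-arm objectives.

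- Adherence: "To compare adherence to behavioral recommendations after the intervention between the intervention and control groups".
- Knowledge of risk factors and symptoms: a comparison "between the intervention and control groups before and after the intervention".
- Risk: "To compare the risk and self-perception of developing breast cancer between the intervention and control groups after the educational intervention".

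Change over time is a separate objective, examined inside each arm. For knowledge it reads: "Evaluate, in each group separately, the knowledge in relation to the risk factors and symptoms of breast cancer before and after the intervention".

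Section 4.3 defines four scores that bear on these objectives: adherence (0 to 12), two knowledge scales (0 to 9 each) and risk perception (6 to 30). All are collected twice: "At both moments, information will be collected related to personal, anthropometric, and behavioral variables". On timing: "The pre-test collection will be carried out after signing the consent and the post-test, after the educational intervention, that is, at 12 weeks".

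Section 5 contains a Kolmogorov-Smirnov check, descriptive statistics, and chi-square and McNemar for qualitative variables. Then comes this sentence: "For qualitative variables, they will be determined based on the distribution of variables". The only model is given as: "Linear regression analyzes will be carried out to determine which variables best predict the score after the intervention". Its outcomes are the knowledge and adherence scores.

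**The concern.** The objectives ask whether the arms differ; section 5 should say how that is answered, and for the scores it does not. The second mention of qualitative variables is probably a slip for quantitative. Read that way, the sentence still only defers the choice to the distribution and names no test, contrast or estimate. The regression asks which variables predict the outcome well, which is not the same as estimating the effect of the intervention. A search for good predictors may drop study group, pre-test score or both.

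No bias is alleged, because a post-test comparison between randomised arms is unbiased. Two things are at stake:

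- No between-arm objective on the scores has a committed effect estimate with a confidence interval.
- The pre-test scores are collected anyway but need not be used to sharpen the comparison. Chance imbalance at baseline is part of this precision loss, not a further cost.

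**Working it through.** **1. The plan's sample size.** Section 4.2 gives 361 women, for a percentage near 75%, ±5 points, 95% confidence, 20% replacements. This reproduces: 1.96² × 0.75 × 0.25 / 0.05² = 288.1; 288.1 / 0.80 = 360.1, rounded up to 361. It is a one-sample precision calculation. It contains no between-arm effect or power, so it does not supply the analysis that section 5 lacks.

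**2. Women per arm (1:1).** If losses are replaced: 361 / 2 = 180. If not: 361 × 0.8 / 2 = 144.

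**3. Assumed inputs.** The documents give no SD, effect size or pre/post correlation *r*. I assume an effect of 0.30 SD, *r* = 0.5 (range 0.3 to 0.7) and a two-sided 5% level; section 5 gives 0.05 without saying one- or two-sided. The comparator is an unadjusted post-test comparison, which is what the adherence and risk objectives describe.

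**4. Formulas.** Adjusting for the pre-test score multiplies the variance by 1 − *r*² = 0.91, 0.75, 0.51 for *r* = 0.3, 0.5, 0.7. Power is that of a two-sample t-test at 0.30 SD, or at 0.30/√(1 − *r*²) when adjusted. The 95% CI half-width is t × √(2/n) × √(1 − *r*²). The equivalent post-only size is n/(1 − *r*²).

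| Per arm | Quantity | Post-only | r = 0.3 | r = 0.5 | r = 0.7 |
|---|---|---|---|---|---|
| 180 | Power | 81.0% | 84.5% | 90.6% | 97.8% |
| 180 | Half-width (SD) | 0.207 | 0.198 | 0.180 | 0.148 |
| 180 | Equivalent n | 180 | 198 | 240 | 353 |
| 144 | Power | 71.8% | 75.8% | 83.4% | 94.4% |
| 144 | Half-width (SD) | 0.232 | 0.221 | 0.201 | 0.166 |
| 144 | Equivalent n | 144 | 158 | 192 | 282 |

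**5. Other effect sizes, r = 0.5.** With 180 per arm, power goes from 47.3% to 58.9% at 0.20 SD and from 96.6% to 99.2% at 0.40 SD. With 144 per arm, it goes from 39.4% to 49.7% and from 92.3% to 97.4%.

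**6. Bounded, discrete scores.** Simulation used rounded, truncated normal scores, 144 per arm, a 0.30 SD latent shift, 4,000 runs per cell and HC3 standard errors for both analyses. Latent means and SDs are assumed.

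| Scale (latent mean, SD) | Post-only, r = 0.3/0.5/0.7 | Adjusted, r = 0.3/0.5/0.7 |
|---|---|---|
| 0–9 (6.0, 1.8) | 69.7 / 68.6 / 70.4% | 74.2 / 80.3 / 91.9% |
| 0–9, strong ceiling (8.5, 1.8) | 58.2 / 58.3 / 59.9% | 59.6 / 66.0 / 79.8% |
| 0–12 (7.0, 2.2) | 71.0 / 70.5 / 71.0% | 74.5 / 81.8 / 93.7% |
| 6–30 (18, 4.5) | 72.4 / 71.6 / 70.8% | 75.9 / 82.5 / 93.9% |

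Type I error of the adjusted analysis was 4.3% to 5.6% over the 12 cells. Discreteness does not undermine the linear model here; a strong ceiling reduces the gain.

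**The case against.** The best defence reads section 5 together with section 3.2.2. The objectives do promise between-arm comparisons. With the probable slip corrected, section 5 promises a test of the scores chosen by their distribution. The regression could contain both study group and pre-test score, and where it did, no precision would be lost for adherence or knowledge. On this view the plan is terse, and the calculated loss is measured against a comparator it never names.

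Part of this stands. The precision figures are conditional on an unadjusted comparison, though that is the natural reading of objectives framed as after the intervention. The gain may also be small: about 4 points at *r* = 0.3, and 1.4 points (58.2% to 59.6%) at *r* = 0.3 with a strong ceiling. No document figure says where in the range the trial lies. The missing effect estimate does not depend on *r*, and an optional predictor in an open search is not a commitment.

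HC3 is a safeguard and not essential: in a check on the 0 to 9 scales at 144 per arm, power with ordinary and HC3 errors differed by at most 0.6 points. The plan places pre-test and randomisation in the same month without stating their order. The point here needs only that the pre-test precedes the intervention, but stating that it is completed before allocation is known would be a useful clarification.

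**Conclusion.** The concern holds and should be acted on. That section 5 commits to no between-arm analysis of the four scores rests on the text alone, and confidence in it is high. The size of the precision loss rests on assumed inputs. At 0.30 SD and *r* = 0.5, power rises by about 10 points with 180 per arm (81% to 91%) and about 12 with 144 (72% to 83%). The interval narrows by 13% (√0.75 = 0.866). Over *r* = 0.3 to 0.7, the adjusted power is 85% to 98% and 76% to 94% respectively. Validity of a post-test comparison is not in question.

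**What to change.** In section 5, before post-test data are seen:

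- For adherence, each knowledge scale and risk perception, specify a linear model: post-test score = study group + pre-test score, with both terms always retained.
- Report the adjusted mean difference between arms with a 95% CI, using HC3 standard errors.
- Make this the between-arm analysis whatever the normality check shows.
- Label the existing prediction regression exploratory.

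Section 4.3 defines no score for estimated risk, so the model covers only the self-perception part of that objective. Which score is primary, and which tests serve the within-group objectives, are separate questions.

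The cost is a few sentences. No objective is reworded and no new data are needed. Section 6 says that the project already has ethics authorisation, so the change may have to be notified. If the software named in section 5 does not provide HC3, the package used should be named.

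### The predictor regressions test an open set of variables against at least three post-test scores at an unadjusted p ≤ 0.05; with 3 to 8 null candidates per outcome, the chance of a false predictor is about 0.3 to 0.65

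*Combined protocol and SAP*

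**What the plan says.** The third paragraph of section 5 (Statistical Analysis) reads: "Linear regression analyzes will be carried out to determine which variables best predict the score after the intervention". The outcomes follow: "knowledge about risk factors, signs-symptoms of early detection of breast cancer, knowledge and adherence to healthy behaviors". Because knowledge appears a second time, this gives three distinct scores, or four if the repeated word means a separate total.

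The last paragraph of section 5 sets one rule for everything: "considering that the results were statistically significant when the value of p is ≤ 0.05".

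Section 5 does not list the candidate variables. The natural pool is the digital form in section 4.3, where "information will be collected related to personal, anthropometric, and behavioral variables (diet and physical activity), self-examination" are followed by the two knowledge scales and then by "perception of risk of developing breast cancer, and barriers to carry out" preventive actions. Section 5 does not say whether randomised group or the pre-test score enters the models. It also does not say whether the models are full, stepwise or built from one-variable screens. None of the specific objectives in section 3.2.2 asks for predictors.

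**The concern.** The stated purpose is to find the best predictors in the data, and the only criterion given is the general p-value threshold. Applied to several variables and several outcomes, that threshold will often yield at least one association that is pure chance. With no exploratory label, the association would be reported on the same footing as any other significant result. It could then be taken as a finding about which women know more or adhere better after the web-app. If variables are also chosen by p-value and then tested on the same data, their p-values and the explained variance will look too favourable.

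Naming a primary comparison between the groups would not settle this, because the predictor tests form a separate family.

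**Working it through.** **1. The plan's own figure.** Section 4.2 states: "A random sample of 361 women will be sufficient to estimate, with 95% confidence and an accuracy of +/- 5 percentage units", for "a population percentage that is expected to be approximately 75" per cent, with 20% replacements. The calculation is 1.96² × 0.75 × 0.25 / 0.05² = 288.1, and 288.1 / 0.80 = 360.1, rounded up to 361. The figure reproduces. It concerns the precision of one percentage and does not limit the error rate examined here. It does suggest about 289 completers, which is used below.

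**2. Inputs.**
- Threshold: p ≤ 0.05 (section 5), taken as two-sided, which the plan does not state.
- Outcomes: 3 (section 5, counting the repeated word once).
- Null candidates per outcome, k: not in the documents. Section 4.3 names nine domains: personal, anthropometric, diet, physical activity, self-examination, two knowledge scales, perceived risk and barriers. Some are an outcome's own pre-test value and probably true predictors. Others may hold several variables. I assume k = 3 to 8.

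**3. Independent tests.** Chance of at least one false predictor = 1 − 0.95^(3k). For k = 3 this is 1 − 0.95⁹ = 0.370, and for k = 8 it is 1 − 0.95²⁴ = 0.708.

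**4. Correlated tests.** Null data were simulated with n = 289, three outcomes and 2,500 runs per setting (Monte Carlo standard error about 0.01). The full-model columns use correlation 0.3 or 0.5 between candidates. The last column tests one variable at a time, with correlation 0.5 between candidates and 0.7 between outcomes.

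| k | Tests | Independent (formula) | Full model, outcome correlation 0.5 | Full model, outcome correlation 0.7 | One at a time |
|---|---|---|---|---|---|
| 3 | 9 | 0.370 | 0.31–0.32 | 0.28–0.29 | 0.29 |
| 4 | 12 | 0.460 | 0.39–0.41 | 0.35–0.36 | 0.33 |
| 5 | 15 | 0.537 | 0.47 | 0.42–0.44 | 0.37 |
| 6 | 18 | 0.603 | 0.53–0.54 | 0.48–0.50 | 0.40 |
| 8 | 24 | 0.708 | 0.65 | 0.57–0.59 | 0.48 |

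With n = 361, candidate correlation 0.3 and outcome correlation 0.5, the full-model results are close: 0.34 at k = 3, 0.53 at k = 6 and 0.64 at k = 8.

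**5. Expected number of false predictors.** This is 3k × 0.05, whatever the correlation: 0.45 at k = 3, 0.9 at k = 6 and 1.2 at k = 8.

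**6. Effect of selection.** Backward elimination gave rates similar to the full model. The chance of a false predictor therefore comes mainly from the number of tests. The further optimism in p-values and explained variance after selection was not quantified.

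**7. Effect of adjustment.** Bonferroni over 24 tests uses 0.05/24 = 0.0021. The familywise chance is then 1 − (1 − 0.05/24)²⁴ = 0.049 under independence, against 0.708 unadjusted.

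**The case against.** The strongest reply is that the documents give no number of candidates, so no rate can be attributed to the plan. That stands. A reader might infer that a false predictor is more likely than not. The text does not support this without a condition: at five null candidates and outcome correlation 0.5 the chance is 0.47, and stronger correlation lowers it. Several section 4.3 variables are also pre-test values of the outcomes. For adherence, the diet and physical activity items make up the score itself. True predictors cannot be false positives.

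Three other strong readings also fail:
- That a promised 5% familywise rate is broken. Section 5 sets a threshold for each result and promises nothing for the family.
- That a fourth outcome makes matters clearly worse. It rests on one repeated word, and a total of the two knowledge scales would add little: about 0.65 to 0.66 at k = 8, almost the same as with three outcomes.
- That the regressions can support no claim of effectiveness. Linear regression is the only method section 5 names that suits the quantitative scores; the other named tests for association are chi-square and McNemar. If group is in these models, its coefficient may be the only baseline-adjusted comparison between the groups.

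It can also be said that a predictor search is self-evidently exploratory and that no objective depends on it. That limits the harm, but section 5 does not say it and applies the same significance rule here as elsewhere.

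**Conclusion.** The concern holds in a conditional form. Section 5 leaves the candidate set and the models open and calls any result significant at p ≤ 0.05 over at least three outcomes. With 3 to 8 truly null candidates per outcome and outcome correlation near 0.5, the chance of at least one false predictor is about 0.3 to 0.65. It exceeds one half from about six null candidates, and from more than six if the outcomes are more strongly correlated. These figures assume two-sided tests, about 289 completers and a value of k that the plan does not supply.

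The conclusion does not depend on passing one half: the low end already makes a chance finding common. The analysis is secondary, so this does not threaten the trial's main comparison, but the correction is cheap and should be made before the data are analysed.

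**What to change.** Rewrite the regression paragraph of section 5 as follows.

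- For each of risk-factor knowledge, signs-and-symptoms knowledge and adherence, fit one prespecified linear model. Force in randomised group and the outcome's own pre-test score. Add a short list of pre-test variables, named in advance. Do not select by p-value.
- Clarify whether the second mention of knowledge is a separate outcome.
- Report every coefficient with its 95% confidence interval.
- State that associations for variables other than group are exploratory and will not be called significant predictors on an unadjusted p ≤ 0.05. State that this label does not demote the group coefficient.
- If significance is claimed for any variable other than group, adjust over all such variables and outcomes, for example by Holm.

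The full model does not by itself lower the rates in the table. It removes the optimism from selection; the label or the adjustment deals with the false predictors. An optimism-corrected R² is optional.

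The cost is a few sentences and a decision on the covariate list, with no new data. The downside is that fewer predictors can be called significant.
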